10.1.2. Device Deficiencies

Device deficiency (DD) information will be collected throughout the study and reported to Medtronic. Note that device deficiencies that result in an adverse device effect (ADE) to the subject should be captured as an Adverse Event only.

10.1.3. Processing Updates and Resolution

For any changes in status of a previously reported AE (i.e. change in actions taken, change in outcome, change in relatedness), information needs to be updated on or added to the original AE e-CRF. All reported adverse events must be followed until the adverse event has been resolved, is unresolved with no further actions planned, the subject exits the study or until study closure, whichever occurs first.

In the event that a subject is exited from the study prior to study closure, all efforts should be made to continue following the subject until all unresolved procedure or system related adverse events, as classified by the investigator, are resolved or they are unresolved with no further actions planned.

At the time of study exit, all AEs with an outcome of "Unresolved, further actions or treatment planned" must be reviewed and an update to the original AE e-CRF must be reported. At a minimum, if there are no changes to the description, relatedness, test and procedures or actions taken, the outcome must be updated to reflect "Unresolved at time of study closure."

10.2. Definitions/Classifications

10.2.1. Adverse Event and Device Deficiency Definitions

Where the definition indicates "device", it refers to any device used in the study.

18 December 2018 Version 4.0

Page 40 of 66

Medtronic

Table 6: Adverse Event Definitions

18 December 2018 Version 4.0 Page 41 of 66

п	
п	Medtronic
п	Meationic

General			
Adverse Event (AE) (Adapted from ISO 14155:2011, 3.2)	Any untoward medical occurrence, unintended disease or injury, or untoward clinical signs (including abnormal laboratory findings) in subjects, users or other persons, whether or not related to the investigational medical device		
	NOTE 1: This definition includes events related to the investigational medical device or the comparator.		
	NOTE 2: This definition includes events related to the procedures involved.		
Adverse Device Effect (ADE)	Adverse event related to the use of an investigational medical device		
(ISO 14155:2011, 3.1)	NOTE 1: This definition includes adverse events resulting from insufficient or inadequate instructions for use, deployment, implantation, installation, or operation, or any malfunction of the investigational medical device.		
	NOTE 2: This definition includes any event resulting from an error use or from intentional misuse of the investigational medical device.		
Device Deficiency (DD) (ISO 14155:2011, 3.15)	Inadequacy of a medical device with respect to its identity, quality, durability, reliability, safety or performance.		
	NOTE: Device deficiencies include malfunctions, use errors and inadequate labeling		
	Relatedness		
Reveal LINQ ICM Procedure Related	An adverse event that occurs that is directly related to the implantation or modification of the Reveal LINQ system.		
Reveal LINQ ICM System Related	An adverse event that results from the presence or performance (intended or otherwise) of any component of the system (including: Reveal LINQ ICM, Programmer, Patient Assistant, and MyCareLink Patient Monitor).		
Cardiovascular Related	An adverse event relating to the heart and the blood vessels or the circulation.		
Seriousness			

18 December 2018 Version 4.0 Page 42 of 66

Medtronic

Complication	An adverse event that results in death, involves any termination of significant device function, or requires invasive intervention.
	Non-invasive: when applied to a diagnostic device or procedure, means one that does not by design or intention: • Penetrate or pierce the skin or mucous membranes of the body, the ocular cavity or the urethra or • Enter the ear beyond the external auditory canal, the nose beyond the nares, the mouth beyond the pharynx, the anal canal beyond the rectum, or the vagina beyond the cervical os For purposes of this part, blood sampling that involves simple venipuncture is considered non-invasive, and the use of surplus samples of body fluid or tissue that are left over from samples taken for non-investigational purposes is also considered non-invasive.
Observation	Any adverse event that is not a complication.
	Note 1: Only system or procedure related AEs will be classified as Complication or Observation.
Serious Adverse Event (SAE) (Adapted from ISO 14155:2011, 3.37)	Adverse event that a) led to death, b) led to serious deterioration in the health of the subject, that either resulted in 5. a life-threatening illness or injury, or 6. a permanent impairment of a body structure or a body function, or 7. in-patient or prolonged hospitalization, or 8. medical or surgical intervention to prevent life-threatening illness or injury or permanent impairment to a body structure or a body function, c) led to fetal distress, fetal death or a congenital abnormality or birth defect NOTE 1: Planned hospitalization for a pre-existing condition, or a procedure required by the CIP, without serious deterioration in health, is not considered a serious adverse event.
	Other
Hospitalization	A therapeutic inpatient hospitalization (excludes outpatient and emergency room visits) lasting greater than or equal to 24 hours.
Stroke	Hemorrhagic or Ischemic stroke with rapid onset of a focal or global neurological deficit or other neurological signs/symptoms consistent with stroke.
Stroke Diagnosis	Diagnosis will be determined by the site's neurologist clinical evaluation and include clinical signs and symptoms consistent with focal or global neurological deficit in addition to one or more of the following: • Neuroimaging procedure (CT, MR, or cerebral angiogram) • Lumbar Puncture (i.e. subarachnoid hemorrhage)

18 December 2018 Version 4.0 Page 43 of 66

Medtronic	

Transient Ischemic Attack (TIA)	-	New focal neurological deficit with rapid symptom resolution (usually 1 – 2 hours), always within 24 hours without tissue injury (based on neuroimaging).		
Unavoidable Adverse Event	o	on Adverse Event inherent to a surgical procedure to a surgical procedure to a ccur in all subjects for a projected duration according to a contract of the co	•	
		Event Description	Timeframe (hours) from the Surgical Procedure	
		Anesthesia related nausea / vomiting	24	
		Low-grade fever (<100°F or 37.8°C)	48	
		Pocket site / Incisional pain	72	
		Mild to moderate bruising / ecchymosis	168	
		Sleep problems (insomnia)	72	
		Back pain related to laying on table	72	
		Shoulder pain/discomfort/stiffness related to shoulder immobilization during procedure	72	

10.2.2. Adverse Events and Deficiency Classification

All reported AEs and DDs will be reviewed by a Medtronic representative. AEs will be classified according to the definitions provided.

Upon receipt of AEs at Medtronic, a Medtronic representative will review the AE/DD for completeness and accuracy and when necessary will request clarification and/or additional information from the Investigator. Medtronic will utilize MedDRA, the Medical Dictionary for Regulatory Activities, to assign a MedDRA term for each adverse event based on the information provided by the investigator.

Regulatory reporting of AEs and DDs will be completed according to local regulatory requirements. Refer to Table 12 and Table 13 for a list of required investigator and Medtronic reporting requirements and timeframes. It is the responsibility of the investigator to abide by any additional AE reporting requirements stipulated by the Ethics Committee responsible for oversight of the study.

For emergency contact regarding a SAE, contact a clinical study representative immediately (refer to the study contact list provided in the site's study documents binder/investigator site file or refer to the contact information provided on the title page).

Adverse Events and Deaths will be classified according to the standard definitions as outlined below:

18 December 2018 Version 4.0

Page 44 of 66

Table 7: Adverse Event Classification Responsibilities

What is classified?	Who classifies?	Classification Parameters
Deletedeses	Investigator	Procedure RelatedSystem Related
Relatedness	Sponsor	Procedure RelatedSystem RelatedCardiovascular Related
	Investigator	SAE
Seriousness	Sponsor	SAE, Complication or Observation (for all system or procedure related adverse events)
Diagnosis	Investigator	Based on presenting signs and symptoms and other supporting data
Diagnosis	Sponsor	MedDRA term assigned based on the data provided by Investigator
Death Classification	Investigator	Sudden Cardiac, Non-sudden Cardiac, Non-Cardiac, Unknown

An independent Clinical Events Committee (CEC) will at minimum conduct a medical review of all endpoint related events for subjects participating in the study. Additionally, the CEC will provide an adjudication of the death classification for all reported deaths.

10.3. Reporting of Adverse Events

Regulatory reporting of AEs/DDs will be completed according to local regulatory requirements. Refer to Table of Adverse Event Reporting Requirements for a list of required investigator reporting requirements and timeframes, and of required Medtronic reporting requirements and timeframes.

The investigator is required to report all SAEs to Medtronic immediately, and to the Ethics Committee per local requirements. Medtronic is also required to report these events to the local regulatory authority based on their requirements. It is the responsibility of the investigator to abide by any additional AE/DD reporting requirements stipulated by the Ethics Committee responsible for oversight of the study.

For AEs/DDs that require immediate reporting, initial reporting may be done by contacting the study sponsor per the sponsor contact information provided in this document.

18 December 2018 Version 4.0 Page 45 of 66

Table 8: AE Reporting Requirements

Serious Adverse Events (SAEs)				
Investigator sul	Investigator submit to:			
Medtronic	Submit in a timely manner after the investigator first learns of the event.			
EC/IRB/MEC	Submit to EC/IRB/MEC per local reporting requirement.			
Regulatory authorities	Submit to regulatory authority per local reporting requirement.			
Sponsor submit	to:			
Regulatory authorities	Submit to regulatory authority per local reporting requirement.			
EC/IRB/MEC	Submit to EC/IRB/MEC per local reporting requirement.			
	All other reportable Adverse Events			
	(System, Procedure, Cardiovascular-Related)			
Investigator sul	omit to:			
Medtronic	Submit in a timely manner after the investigator first learns of the event.			
EC/IRB/MEC	Submit to EC/IRB/MEC per local reporting requirement.			
Regulatory authorities	Submit to regulatory authority per local reporting requirement.			
Sponsor submit	to:			
Regulatory authorities	Submit to regulatory authority per local reporting requirement.			
EC/IRB/MEC	Submit to EC/IRB/MEC per local reporting requirement.			
Device Deficiencies				
Investigator sul	omit to:			
Medtronic	Submit in a timely manner after the investigator first learns of the event.			
EC/IRB/MEC	Submit to EC/IRB/MEC per local reporting requirement.			
Regulatory authorities	Submit to regulatory authority per local reporting requirement.			

10.3.1. Subject Death

10.3.1.1. Death Data Collection

All subject deaths must be reported by the investigator to Medtronic using an AE e-CRF as soon as possible after the investigator first learns of the death. The AE leading to death must be reported and will document the death as the outcome.

For subjects with a Reveal LINQ ICM

18 December 2018 Version 4.0 Page 46 of 66

In the event of a subject's death, the inserted device should be explanted and returned to Medtronic for analysis whenever possible. Local laws and procedures must be followed where applicable.

System Interrogation Data Recommendations:

 After the subject has died but prior to explant, the device shall be interrogated and a full summary interrogation (Interrogate All) performed when possible.

If the device is not interrogated, an explanation must be entered on the AE form. If any system component is returned to Medtronic, internal return product reporting systems may be used to gather additional information about the returned device/component.

A copy of the death certificate, if available and allowed by state/local law, should be sent to the Medtronic clinical study team. When a death occurs in a hospital, a copy of the death summary report and all relevant hospital records should be sent to the Medtronic clinical study team, if available. If an autopsy is conducted, the autopsy report should also be sent to the Medtronic clinical study team if available and allowed by state/local law. When the death occurs at a remote site, it is the investigative site's responsibility to attempt retrieval of information about the death. In summary, the following data will be collected:

- Date of death
- Detailed description of death
- Cause of death
- Relatedness to system and/or procedure (subjects with Reveal LINQ inserted)
- Device interrogation (if available, subjects with a Reveal LINQ ICM)
- Death summary/hospital records (if available and allowed by state/local law)
- Autopsy report (if available and allowed by state/local law)
- Death certificate (if available and/or allowed by state/local law)

18 December 2018 Version 4.0 Page 47 of 66

10.3.1.2. Death Classification and Reporting

Sufficient information will be required in order to properly classify the subject's death. The Investigator shall classify each subject death per the following definitions:

Table 9: Subject Death Classification

Classification	Definition
Cardiac Death	A death directly related to the electrical or mechanical dysfunction of the heart
Sudden Cardiac Death (SCD)	Natural death due to cardiac causes, indicated by abrupt loss of consciousness within one hour of the onset of acute symptoms; preexisting heart disease may have been known to be present, but the time and mode of death are unexpected. If time of onset cannot be determined, SCD will alternatively be defined as any unexpected cardiac death occurring out of the hospital or in the emergency room as dead on arrival.
Non-sudden Cardiac Death	All cardiac deaths that are not classified as sudden deaths, including all cardiac deaths of hospitalized subjects on inotropic support.
Non-cardiac Death	A death not classified as a cardiac death
Unknown	There is insufficient or inadequate information to classify the death.

The Clinical Events Committee (CEC) will review deaths and provide a final adjudication of the primary cause of death and death classification.

Regulatory reporting of Subject Deaths will be completed according to local regulatory requirements. Refer to Table 12 and Table 13 for a list of required investigator and sponsor reporting requirements and timeframes.

10.4. Product Complaint Reporting

Product complaint reporting is applicable to any Medtronic market released product, regardless of subject's participation in a clinical study.

All devices used in the study are market-released, product complaint reporting is applicable. This includes when an AE is related to a market-released device during the study. The reporting of product complaints is not part of the clinical study and should be done in addition to the AE reporting requirements. Refer to local regulations for reporting requirements.

Product Complaint: Any written, electronic or oral communication that alleges deficiencies related to the identity, quality, durability, reliability, safety, effectiveness or performance of a medical device that has been placed on the market.

It is the responsibility of the investigator to report all product complaint(s) associated with a medical device distributed by Medtronic, regardless whether they are related to intended use, misuse or abuse of the product. Reporting must be done immediately and via the regular channels for market-released

18 December 2018 Version 4.0 Page 48 of 66

products. The reporting of product complaints by the clinical study team must be done according to local Standard Operating Procedures.

Medtronic will notify the regulatory authorities (e.g. Competent Authority) as applicable for the following incidents immediately upon learning of them:

- Any malfunction or deterioration in the characteristics and/or performance of a device, as well as any inadequacy in the labeling or instructions for use which led or might have led to the death or serious deterioration in the state of health of a patient, user, or other person.
- Any technical or medical reason resulting in withdrawal of a device from the market by the manufacturer.
- A serious deterioration in the state of heath includes:
 - Life-threatening illness or injury
 - o Permanent impairment of a body function or permanent damage to a body structure
 - o In-patient or prolonged hospitalization
 - Medical or surgical intervention to prevent life-threatening illness or injury or permanent impairment to a body structure or a body function
 - o Fetal distress, fetal death or a congenital abnormality or birth defect

11. Data Review Committees

The Stroke AF study will utilize a Steering Committee for study design and oversite, a CEC for the assessment of Adverse Events and recurrent stroke/TIA data, an Endpoint Adjudication Committee (the CEC may serve as the EAC) for an independent review of endpoint (AF) and a Publication Committee to manage study publications.

Committee membership rosters will be maintained at Medtronic and will be made available upon request

11.1. Clinical Events Committee (CEC) Review

At regular intervals, an independent Clinical Events Committee (CEC) will at minimum conduct a medical review (adjudicate) of reported arrhythmias including AF episodes/events as well as reported strokes/TIAs and deaths for subjects participating in the study.

The CEC will consist of a minimum of three (3) non-Medtronic employed physicians that are not participating investigators for the study, including a CEC chairperson. At least three CEC members must adjudicate, at a minimum, all deaths and endpoint related events. All other AEs may be adjudicated by at least one physician member of the CEC.

Medtronic personnel may facilitate and participate in a CEC meeting but will be non-voting members.

18 December 2018 Version 4.0 Page 49 of 66

Medtronic

For adverse events and deaths reviewed by the CEC, Medtronic will provide the CEC with the Investigator's description and classification. The CEC is responsible for reviewing the Investigator's assessment and supportive documentation (when available), reviewing applicable definitions, and determining final classifications for all adjudication parameters. Additionally, the CEC will provide an adjudication of the death classification for all reported deaths including primary cause of death.

If the CEC disagrees with the investigator's classification of the event, the rationale will be provided to the investigator. If the investigator agrees with the CEC's adjudication, the case report form documenting the AE will be updated accordingly.

If the investigator does not agree with the CEC's adjudication classification, both determinations will be provided within the final report; however the CEC's adjudication will be used for data analysis. The disagreement will also be included in reporting to ethic committees and regulatory authorities, if required.

12. Statistical Design and Methods

Medtronic employees or designees will perform all statistical analyses. Additionally, a separate Statistical Analysis Plan (SAP) will be developed to further describe statistical methods, pre-specified data handling rules, and pre-specified analyses that will be included in study reports. Any change to the data analysis methods described in the CIP will require an amendment only if it changes a principal feature of the CIP. Any other change to the data analysis methods described in the CIP, and the justification for making the change, will be described in the clinical study report. Additional exploratory analyses of the data may be conducted as deemed appropriate. Missing data will not contribute to the objectives unless specified otherwise within the analysis methods.

The study has been powered for the primary objective (see sample size determination for the primary objective below), to be evaluated after 12 months of follow-up have been completed. The primary objective data and applicable ancillary objective data will be provided in a 12 month report. Secondary objective data, and remaining ancillary objective data will be provided in a final report. Ancillary objects are considered exploratory. There will be no correction for multiple testing. Intent-to-treat principles will be used for analyzing each of objectives unless otherwise specified.

12.1. Primary Objective

The primary objective is to compare the incidence rate of AF through 12 months between the continuous monitoring arm vs control arm in subjects with a recent ischemic stroke of presumed known origin.

18 December 2018 Version 4.0 Page 50 of 66 Medtronic

i. Hypothesis

 H_0 : $h_C(t) = h_T(t)$ for $t \le 12$ months

• H_A : $h_C(t) \neq h_T(t)$ for $t \leq 12$ months

• where $h_T(t)$ and $h_C(t)$ are the hazard functions of first detected and adjudicated AF at time t for subjects with and without the Reveal LINQ diagnostics for AF, respectively.

ii. Endpoint Definition

AF will be defined as an AF event lasting more than 30 seconds. The first AF episode detected and adjudicated by the endpoint adjudication committee will be used for this analysis.

iii. Performance Requirements

The null hypothesis will be rejected if the two-sided log-rank test p-value is less than 0.05.

iv. Rationale for Performance Criteria

The exact rate of AF is unknown in this population. Data from the CRYSTAL AF study and Rabinstein et al (2013) has been used to estimate the 12 month incidence rate of AF in patients with an ischemic stroke of presumed known origin.

The incidence rate of AF through 12-months was 12.4% in the continuous monitoring arm in the CRYSTAL AF study which was conducted in patients with a cryptogenic stroke.

Rabinstein et al (2013) used prolonged ambulatory cardiac monitoring to assess the incidence rate of paroxysmal AF through 3 weeks in patients with a cryptogenic stroke and patient with a stroke of presumed known cause. The incidence rate of paroxysmal AF through 3-weeks was 25% in the patients with a cryptogenic stroke and 14% in patients with an ischemic stroke of presumed known origin.

The above incidence rates were used to estimate the 12 month incidence rate of AF in patients with ischemic stroke of presumed known origin. We expect the AF incidence rate to be lower in patients with an ischemic stroke of presumed known origin when compared to the incidence rate in patients with a cryptogenic stroke. Consequently, an AF incidence rate of 8% through 12 months is expected in our continuous monitoring arm. An AF incidence rate of 2% through 12 months is expected our control arm. This is the same rate observed in the control arm for the CRYSTAL AF study. Although we expect the AF incidence rate to be lower in patients with an ischemic stroke of presumed known origin, we also expect that present standard of care treatment includes more rhythm monitoring then it did during the time of the CRYSTAL AF study.

The objective of the study is to compare the incidence rate of AF through 12 months between the continuous monitoring arm vs control arm in subjects with a recent ischemic stroke of presumed known origin.

18 December 2018 Version 4.0 Page 51 of 66 Medtronic

v. Sample Size Determination

- A total of 23 events are required to demonstrate that the hazard rates are different between the two arms. Approximately 496 subjects will be enrolled. Assuming 2% attrition from enrollment to randomization, approximately 486 subjects will randomized. Subjects will be followed for 3 years, until end of device life or until official study closure, whichever occurs first. Withdrawn subjects will not be replaced.
- The assumptions used for the calculations were:
 - Two-sided log-rank test
 - Alpha = 0.05
 - 85% power
 - Annual Attrition rate = 10%
 - Annual Crossover rate = 5%
 - Follow-up Time = 1 year
 - Event-free one-year survival rate of 92% in the continuous monitoring arm
 - Event-free one-year survival rate of 98% in the control arm (hazard ratio of 4.13)

The procedure "Logrank tests (Lakatos) using proportion surviving" in PASS 2008 was used to calculate the number of events required to test this objective.

vi. Analysis Methods

Arrhythmic episodes recorded by the subject's inserted/implanted device or from external monitoring will be adjudicated by the adjudication committee to determine if they meet the primary endpoint definition. Only first detected and adjudicated AF episodes within 12-months (365 days) will be included for analysis. Each subject's time to first detected and adjudicated AF will be defined as the time from randomization date to the date of first documented AF (i.e. the date of event per Reveal LINQ ICM, ECG, etc) to meet the primary endpoint definition, and Kaplan-Meier curves will be generated for each randomization arm. Subjects who have not experienced an AF endpoint through 12 months will be censored at:

- their point of last contact, usable Reveal LINQ ICM interrogation or CareLink transmission if they occur before 12 months, whichever is later or
- 12 months if their point of last contact, usable Reveal LINQ ICM interrogation or CareLink transmission go beyond 12 months.

A two-sided log-rank test will be performed to compare the rates between arms.

In addition to the analysis on the full population, subgroup analysis for subjects with small vessel disease stroke and large vessel cervical or intracranial atherosclerosis stroke will be presented.

- vii. Determination of Patients/Data for Analysis
- All randomized subjects will be included in the analysis.

18 December 2018 Version 4.0 Page 52 of 66

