5.1. Study Design

Stroke AF is a prospective, multi-site, randomized, controlled, non-blinded, post-market study. The Stroke AF study will compare the incidence rate of AF through 12 months between the continuous monitoring arm and the control arm in subjects with a recent ischemic stroke of presumed known origin. Once enrolled, subjects will be randomized 1:1 (continuous monitoring vs control). Subjects randomized to the continuous monitoring arm will have a Reveal LINQ ICM inserted within 10 days of the qualifying stroke and undergo continuous remote monitoring. Subjects randomized to the control arm will be followed per site specific standard of care.

The study is expected to be conducted at approximately 40 sites located in the United States (U.S.).

It is estimated that approximately 496 subjects will be enrolled in the study. Assuming 2% attrition from enrollment to randomization, approximately 486 subjects will have randomized. A total of 23 first documented AF events within 12 months of randomization are required for the study to test the primary objective. AF will be defined as an AF event lasting more than 30 seconds and adjudicated by the endpoint adjudication committee. The analysis of the primary objective will occur after all enrolled subjects have completed 12 months of follow-up. Approximately 248 devices may be used in the study. Based on previous studies of this scope and magnitude, it is estimated that sites may identify and enroll on average one eligible subject per month.

To ensure a widespread distribution of data and minimize site bias in study results, the maximum number of subjects who may be enrolled at a single site is 50 subjects. Sites that enroll faster than others will be allowed to do so in order to maintain an adequate overall study enrollment rate. In addition, to ensure a robust dataset is available for subgroup analysis, a maximum of 50% (approximately248) subjects with lacunar stroke (i.e., small vessel disease) may be enrolled. Medtronic will notify study sites when enrollment of lacunar stroke subjects is no longer allowed, if applicable.

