### 4.3. Primary and final reports

The objectives for the primary report can be analyzed after all enrolled subjects have 1) had their 12month visit, 2) missed the 12-month visit and the 12-month visit window has closed, or 3) exited prior to the 12-month visit window closing. A data snapshot will be used to analyze data for the primary report since follow-up will continue. Once follow-up is complete and the study data collection and cleaning is finalized, a second data snapshot will be used to analyze data for the final report.

Table 1 shows which objectives will be analyzed for the primary and final reports. All objectives will be included in the final report using the final data snapshot.

| l able 1 | L: Objective | s analyzed fo | or the primary | and final reports |
|----------|--------------|---------------|----------------|-------------------|
|          |              |               |                |                   |

| Objective           | Primary Report | Final Report |
|---------------------|-----------------------|--------------|
| Primary Objective   | Х                     | Х            |
| Secondary Objective |                       | Х            |

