# 6. Determination of Sample Size

### 6.1. Primary Objective

A total of 23 first events across the two treatment groups are required to demonstrate the primary objective of the study. Assuming 2% attrition from enrollment to randomization, approximately 486 subjects will be randomized. Subjects will be followed for 3 years, until end of device life or until official study closure, whichever occurs first. However, the primary objective of the study, upon which this sample size calculation is based, will be analyzed considering data up to the 12 months follow-up visit for all subjects in the study at the time of the analysis. This sample size calculation then assumes a follow-up time equal to 1 year and an accrual time equal to zero (data from all subjects is analyzed from randomization to the 12th month follow-up visit, regardless of how long they've been in the study at the time of the analysis). Withdrawn subjects will not be replaced.

The assumptions used for the calculations were:

- Two-sided log-rank test
- Alpha = 0.05
- 85% power
- Annual Attrition rate = 10% (in each treatment group)
- Annual Crossover rate = 5% (in each treatment group)
- Follow-up Time = 1 year
- Event-free one-year survival rate of 92% in the continuous monitoring arm
- Event-free one-year survival rate of 98% in the control arm (hazard ratio of 4.13)

This document is electronically controlled. Printed copies are considered uncontrolled.

Version 2.0 15/MAY/2017

The procedure "Logrank tests (Lakatos) using proportion surviving" in PASS 2008 was used to calculate the number of events required to test this objective.

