### *iii. Performance Requirements*

The null hypothesis will be rejected if the two-sided log-rank test p-value is less than 0.05.

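### Do the protocol's own sample-size inputs fail to give the stated 85% power with 486 randomized subjects and 23 events?

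*Protocol*

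**What the plan says.** Protocol section 12.1.v and SAP section 6.1 give the same calculation. The protocol states its result as "A total of 23 events are required to demonstrate that the hazard rates are different between the two arms", with about 486 subjects randomized. The outcome assumptions are "Event-free one-year survival rate of 92% in the continuous monitoring arm" and "Event-free one-year survival rate of 98% in the control arm (hazard ratio of 4.13"). Both documents list 10% annual attrition, 5% annual crossover, two-sided alpha of 0.05 and 85% power. The SAP adds that both annual rates apply to each arm, "Annual Crossover rate = 5% (in each treatment group"), and fixes the time frame: "This sample size calculation then assumes a follow-up time equal to 1 year and an accrual time equal to zero". Both name the Lakatos log-rank procedure in PASS 2008. Neither states which variance form or how many time intervals were used.

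On the event count, Protocol section 5.1 says "A total of 23 first documented AF events within 12 months of randomization are required for the study to test the primary objective", and SAP section 3 repeats this. The same paragraph of section 5.1 sets the primary analysis for when every enrolled subject has completed 12 months. SAP section 4.3 has a matching rule, which begins "The objectives for the primary report can be analyzed after all enrolled subjects have" and then lists the 12-month visit held, missed with its window closed, or the subject exited. The decision rule is "The null hypothesis will be rejected if the two-sided log-rank test p-value is less than 0.05".

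**The concern.** A reader who codes the Lakatos model in its common single-variance form and enters the listed inputs gets 80.3% power at 486 subjects. That form needs about 552 subjects and 26.2 events for 85%. It comes near 85% at 486 (84.1%) only when crossover is left out, so it is natural to suspect that crossover was listed but never entered. Simulation of the planned test, at about 83%, also falls short of 85%.

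If the suspicion were right, the figure on which the sample size rests would be wrong, the type II error would be nearer 20% than 15%, and the listed inputs could not be trusted.

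The word used for the 23 events adds to the doubt. Read literally, it would make the primary test depend on a count that neither the analysis trigger nor the rejection rule mentions.

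**Working it through.** **Inputs** (Protocol 12.1.v; SAP 6.1 for the per-arm rates and zero accrual): 1:1 allocation, N = 486, follow-up 1 year, accrual 0, attrition 10% per year per arm, crossover 5% per year per arm to the other arm's hazard, two-sided alpha 0.05 (z = 1.96), 85% power (z = 1.036).

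**Hazards.** Monitoring: −ln(0.92) = 0.08338 per year. Control: −ln(0.98) = 0.02020 per year. Ratio 0.08338 / 0.02020 = 4.13, as stated.

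**Enrolment.** 486 / 0.98 = 495.9, which gives the stated 496.

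**Markov model.** The year is cut into 400 intervals and each arm is followed through the states lost, event, active on monitoring and active on control. Summed over the year, the event probability is 0.0746 in the monitoring arm and 0.0204 in the control arm. With 243 per arm, the expected events are 18.13 + 4.96 = d = 23.09.

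**Log-rank quantities.** In each interval let φ be the ratio of numbers at risk (monitoring to control), θ the ratio of hazards after crossover, and r the share of all events. Then:

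- mean score per event: g = Σ r [φθ/(1+φθ) − φ/(1+φ)] = 0.2926
- null variance per event: V0 = Σ r φ/(1+φ)² = 0.2499
- alternative variance per event: V1 = Σ r φθ/(1+φθ)² = 0.1685

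V1 is well below V0 because, at an average diluted hazard ratio of 3.77, an event falls in the monitoring arm with probability of about 3.77/4.77 = 0.79. Then 0.79 × 0.21 = 0.166, against 0.5 × 0.5 = 0.25 under the null.

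**Plan's figure, two-variance form.**

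- Power = Φ[(√d · g − 1.96√V0) / √V1] = Φ[(4.805 × 0.2926 − 1.96 × 0.4999) / 0.4105] = Φ(1.037) = **85.0%**
- Events for 85% = [(1.96√V0 + 1.036√V1) / g]² = [(0.980 + 0.425) / 0.2926]² = **23.07**
- N for 85% = 23.07 / [(0.0746 + 0.0204)/2] = **485.7** (from unrounded values)

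These are the stated 85%, 23 and 486. Letting subjects cross back gives 85.1%, 23.03 events and 484.8 subjects. With 4,000 intervals power is still 85.0%; with 12 intervals it is 85.4%.

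**Single-variance form.**

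- Power = Φ(√d · g / √V0 − 1.96) = Φ(2.812 − 1.96) = Φ(0.852) = **80.3%**
- Events for 85% = (1.96 + 1.036)² × V0 / g² = 26.2, so N is about 552

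Inputs, model and expected events are the same; only the variance in the power term differs.

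**Was crossover entered?** Two-variance power at N = 486:

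| Annual crossover per arm | Power |
|---|---|
| 0% | 89.4% |
| 2.5% | 87.3% |
| 5% (stated) | 85.0% |

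In the form that recovers the plan, the stated 5% gives 85%, and leaving crossover out moves power away from it.

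**Simulation.** The log-rank test with all listed inputs at N = 486 rejects in 83.0% to 83.3% of trials across separate runs (20,000 to 160,000 replicates), with about 23.1 events on average. Power reaches 85% at about N = 510.

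**The case for a change.** The strongest reply is that the trial will be judged by the log-rank test itself, not by a formula for it. Simulated power is about 83%, several runs agree, and so the shortfall of about two points is not noise. The documents also leave out the variance form, although the two forms differ by about five points at this hazard ratio (85.0% − 80.3% = 4.7). A reader therefore cannot confirm the 85% without trying both. This much is true. It shows that a normal approximation runs slightly high with some 23 events and a hazard ratio near 4. But the plan attributes its 85% to a named large-sample procedure, and that figure is recovered. Two points is also small beside the uncertainty in the event rates: Protocol section 12.1.iv itself says the AF rate in this population is not known.

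The second reply concerns the event count. On the plan's own assumptions about 46% of simulated trials end with fewer than 23 events, and 77% of those still reject. Taken literally, the sentence in Protocol section 5.1 and SAP section 3 would put the test in doubt in nearly half of trials that go as assumed. The wording is loose, but 23 is the number needed for 85% power, which is ordinary sample-size usage. The trigger is completed 12-month follow-up, and the rejection rule sets no minimum number of events. No reader following those rules would withhold the test.

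**Conclusion.** The concern does not hold. From the listed inputs, the two-variance Lakatos calculation gives 85.0% power at 486 randomized subjects and needs 23.07 events and 485.7 subjects for 85%. There is no sign that crossover or any other input was misreported, and no basis for saying that 552 subjects are needed. Restating the power as about 80% would replace a figure that can be recovered with one lying below even the simulated power of about 83%.

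This rests on one inference: that PASS 2008 used the two-variance form. PASS was not run and the documents do not name the form. The simultaneous match on subjects, events and power is the evidence. What remains is a two-point difference between approximation and simulation, and an editorial looseness in calling the 23 events required. Neither affects the sample size, alpha, the test or its timing.
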